7.0 PATIENT EVALUATION

Every effort will be made to adhere to the schedule of events and all protocol requirements. Variations in schedule of events and other protocol requirements that do not affect the rights and safety of the patient will not be considered as deviations. Such variations may include laboratory assessments completed outside of schedule, occasional missed required research samples such as correlative assays.

7.1 Pre-Treatment Evaluation

All pretreatment studies should be obtained within 14 days of entry into the trial, unless otherwise stated.

- 7.1.1 A complete history and physical, documentation of all measurable disease, concomitant medications and performance status.
- 7.1.2 CBC, platelet count, differential (differential can be omitted if WBC is $\leq 0.5 \times 10^9/L$).
- 7.1.3 Creatinine, total bilirubin, ALT or AST, sodium, potassium, chloride, glucose, uric acid, bicarbonate, BUN, calcium, magnesium, alk phos, direct bili.
- 7.1.4 Pregnancy test (urine or plasma) in females of childbearing potential should be performed within 72 hours before initiation of protocol therapy.
- 7.1.5 Bone marrow biopsy/aspirate during the last 28 days preceding study initiation. Cytogenetics will be obtained prior to therapy (results from prior analysis can be used for this purpose).

7.1.6 Pretreatment optional correlative studies (see below)

7.1.7 Electrocardiogram (EKG)

7.1.8 Routine urinalysis

7.1.9 Chest X-ray

7.1.10 TSH, free T3, free T4, free & total cortisol

7.1.11 Respiratory PCR panel

7.2 Evaluation During Treatment

7.2.1 Physical exam at the start of each cycle (± 4 days) and documentation of all concomitant medications.

7.2.2 CBC, platelet count, differential twice weekly (± 4 days) for the first 3 cycles, then every 2-4 weeks (differential can be omitted if WBC is $\leq 0.5 \times 10^9/L$)

7.2.3 Creatinine, total bilirubin, ALT, or AST, calcium, magnesium, glucose, BUN, uric acid, fractionated bilirubin, alkaline phosphatase, sodium, potassium, chloride, bicarbonate twice weekly (± 4 days) for the first 3 cycles, then every 2-4 weeks.

7.2.4 TSH, free T3, free T4, and free & total cortisol once monthly (± 4 days) for the first 3 cycles, then every 3 months (± 4 days).

7.2.5 Bone marrow aspiration on day 28 (± 7 days), then every 1-4 cycles. Bone marrow tests can be ordered more frequently if mandated by development of peripheral blood counts. No repeat bone marrow is necessary if nonresponse or progressive disease can be unequivocally diagnosed from peripheral blood tests or, in patients with a WBC < 0.3 if the bone marrow test is considered noncontributory by the investigator at any time point.

7.2.6 Concomitant medication data will not be collected or entered into the case report form except for concomitant hydroxyurea; however, the subject's medication record will contain a list of concomitant medications.

Correlative Studies relating to immunologic response (Optional):

Tumor tissue, blood samples and bone marrow aspirate will be collected from patients under Z20160444 and will be sent to [name] lab at MD Anderson for research

purposes (described below). Patients will be consented separately on this IRB approved consent for collection of additional material. Correlative laboratory studies will be conducted under this clinical trial protocol as described below.

7.2.7 Patients may participate in the clinical study protocol irrespective of whether they choose to participate in the correlative studies. In tumor tissues, immunohistochemical studies will be performed to evaluate tumor and immunological cell markers such as CD4 and CD8 T cells. In peripheral blood, we will also evaluate tumor and immune cell populations including but not limited to CD4 and CD8 T cells in pre and post therapy samples.

Proposed correlative studies to be performed:

- Standard of Care tests done on all AML patients at MDACC: To analyze for the presence of common somatic mutations, we routinely perform a 53-gene/28-gene panel with validated, next-generation platform sequencing on DNA extracted from bone marrow samples in the CLIA-certified molecular laboratory at MD Anderson Cancer Center at pre-treatment and end of study (if available) assessment for all AML patients at MDACC. Multiparametric flow-cytometry for minimal residual disease (MRD) assessment in AML by validated 15 color flow cytometry, cytogenetics, FISH and molecular markers (if mutated at baseline) at baseline and on treatment to assess for MRD will be done routinely at MDACC Hematopathology lab as standard of care. These data will automatically be available for all patients and will allow exploration of correlations between specific somatic mutations and/or cytogenetic aberrations and response in AML patients.
- Multi-stain immunohistochemistry and validated immune relevant multiparametric flow-cytometry on bone marrow and peripheral blood at the above mentioned time-points on all patients to: (a) identify the immunophenotype of tumor-infiltrating T-lymphocytes (TIL): CD8+, CD4+ effector, or CD4+ regulatory, (b) determine the quantitative expression of immune ligands on AML blasts, MSCs and (c) determine the quantitative expression of positive and negative co-stimulatory molecules on TILs pre- and post-therapy with the combination. For the analysis of the co-stimulatory ligands on leukemic blasts (defined as CD13+HLADR+CD33+CD38+), we have developed the “AML tumor ligand panel”: 4-1BBL, B7-1, B7-2, ICOSL, PDL-1, PDL-2, OX40L, CD40, CD27L, and CD137L. For the analysis of co-stimulatory molecules on T cells (CD4 T effector cells defined as CD3+CD4+Foxp3- cells; CD4 T regulatory cells defined as CD3+CD4+CD127-Foxp3+ cells, and CD8 T cells defined as CD3+CD8+) we have developed the “AML lymphocyte panel”: 4-1BB, CTLA-4, CD28, ICOS, PD-1, OX40, CD40L, LAG-3 and TIM-3. These studies may enable identification of prognostic and

predictive markers and enable the identification of other immune checkpoints of significance for future checkpoint based therapeutic approaches in AML. These studies may be performed in the Department of Leukemia and Immunotherapy platform using validated MFC (or Cytof panels that we are currently validating) or through Pfizer commercial vendors depending on the more financially viable option.

Peripheral blood (up to 45 mL within 24 hours: about 3 tablespoons) will be collected in patients who consent to the correlative studies for testing of biomarkers at the following time points:

- Baseline (prior to 5-azacytidine dose), on day 14 (prior to avelumab dose #2), and on day 28 (+/- 5) on cycle 1 (done at MD Anderson).
 - In cycle 2 blood sample will be obtained on day 14 (prior to Avelumab dose) when possible.
 - In cycle 4, 8, and 12 blood samples will be obtained on day 1 (prior to 5-azacytidine dose) and day 14 (prior to avelumab dose) when possible.
- All these tests can be +/- 5 days.
- Samples will be collected at progression whenever possible.

Bone marrow samples will be collected in patients who consent to the correlative studies for testing of biomarkers at baseline, at day 28 (+/-5 days), at day 28 (+/- 5 days) of cycles 3, 7, and 11, and at progression (if possible).

All correlative samples are optional.

Missed samples for correlative studies will not constitute protocol deviations.

- 7.2.8 For patients that remain on study with no significant toxicity for more than 6 months, subsequent evaluations during study may be modified after discussion with the principal investigator. These include a decrease in frequency of bone marrow aspirations to every 6-12 months (or as clinically indicated), correlative studies to every 6-12 months (or suspension of sample collection for correlative studies), other laboratory tests to once every cycle.
- 7.2.9 ALL treatments with avelumab must be administered at the MDACC outpatient clinic. The first cycle of azacytidine must be administered at the MDACC outpatient clinic. Subsequently, patients will have the option of receiving 5-azacytidine injections or infusions at the MDACC outpatient clinic or local ambulatory treatment center. We do not intend for the subjects to receive avelumab at any time at an outside physician's office. During the first cycle all the laboratory

evaluations will be done at MDACC. Subsequently, the patient may have the laboratory work done at a local clinic and the results reported and filed by the MDACC research nurse for the study. The laboratory work done at the local clinic will be forwarded to the patient's attending physician at MDACC or PI of the study, who will sign off on the labs to verify that the results have been reviewed.

7.2.10 EKG beginning Cycle 2 on Day 1 (+/- 5 days) for subsequent cycles.

7.2.11 Urinalysis beginning Cycle 2 on Day 1 (+/- 5 days) for subsequent cycles.

Outside Physician Participation During Treatment

1. MDACC Physician communication with the outside physician is required prior to the patient returning to the local physician. This will be documented in the patient record.
 2. A letter to the local physician outlining the patient's participation in a clinical trial will request local physician agreement to supervise the patient's care (**Appendix F**).
 3. Protocol required evaluations outside MDACC will be documented by telephone, fax or e-mail. Fax and/or e-mail will be dated and signed by the MDACC physician, indicating that they have reviewed it. Changes in drug dose and/or schedule must be discussed with and approved by the MDACC physician investigator, or their representative prior to initiation, and will be documented in the patient record.
 4. A copy of the informed consent, protocol abstract, treatment schema and evaluation during treatment will be provided to the local physician.
 5. Documentation to be provided by the local physician will include progress notes, reports of protocol required laboratory and diagnostic studies and documentation of any hospitalizations.
 6. The home physician will be requested to report to the MDACC physician investigator all life threatening events within 24 hours of documented occurrence.
 7. All follow-up visits will be performed at MDACC.
 8. Changes in drug dose and/or schedule must be discussed with and approved by the MDACC physician investigator, or their representative prior to initiation, and will be documented in the patient record.
- 7.2.12 Patients with an objective response at completion of active study treatment will be followed for survival at MD Anderson Cancer Center (MDACC) every 3 to 6 months for up to 5 years after completion of active treatment and while still on study. If the patient

is unable to return to MDACC the follow-up visits may be conducted via telephone. Every 3-6 months for up to 5 years after last dose of study drug patient will have a physical exam and blood (about 1-2 teaspoons) will be drawn for routine testing. If the patient is unable to return to MD Anderson, they may be called by a member of the research staff and asked how they are feeling.

Table 6. The study assessment schema is shown in tabular form below

Study Period/Cycle	Screening*	Treatment																	End of Study (EOS) ^{h,i}	Long-Term Follow-Up	
		Cycle 1						Cycle 2						Cycle 3							Subsequent Cycles ^k
Cycle Day		1	8	14	15	22	28	1	8	14	15	22	28	1	8	14	15	22	1	30 Days After Last Dose	Every 3-6 months
Study Day	-14 to 0	1	8		15	22		29	36		43	50		57	64	70	71	78	—		
Complete history	X	X						X						X					X		
Physical examination ^a	X	X						X						X					X	X	
Vital Signs ^{**}		X		X				X		X				X		X			X		
Performance status	X	X						X						X					X	X	
Document all measurable disease (if present)	X																				
Concomitant medications ^a	X	X						X						X					X		X
ECG ^l	X							X						X					X		
CBC with differential ^b	X	X	X		X	X		X	X		X	X		X	X		X	X	X	X	
Sodium, Potassium, Chloride, glucose, uric acid, bicarbonate, BUN, Creatinine, total bilirubin, direct bilirubin, calcium, magnesium, ALT ₇ or AST, alk phos ^b	X	X	X		X	X		X	X		X	X		X	X		X	X	X	X	
Routine Urinalysis	X	X						X						X					X		
TSH, free T3, free T4 ^c , free & total cortisol		X						X						X					X		
Pregnancy test ^d	X																				
Bone marrow aspirate/biopsy ^e	X						X												X		

Correlative	Screening	Cycle 1				Cycle 2				Cycle 3				Subsequent cycles	EOS
Optional correlatives on blood ^f	X			Day 14	Day 21-28			Day 14		No		No		Day 1 and 14 of cycles 4, 8, 12	If possible
Chest X-ray	X														
Respiratory PCR panel	X														
Optional correlatives on bone marrow ^g	X				C#1 Day 28			C#2 Day 28				C#3Day 28	Day 28 of cycle 6, 12	If possible	

* Samples collected at screening do not need to be repeated on Day 1 of Cycle 1.

** During the first infusion patient vital signs should be monitored prior to dosing, approximately 15 minutes after initiation of the infusion (then approximately every 15-20 minutes as indicated), at approximately 60 and 120 minutes after completion of the infusion, or longer if indicated, until the vital signs normalize or return to baseline. For subsequent infusions, vital signs should be collected prior to dosing, approximately every 30 minutes during dosing, and approximately 1 hour post dosing.

^a A complete physical examination and documentation of concomitant medications will be done on day 1 of each cycle (+/- 4 days).

^b The specified labs must be done at least twice weekly (+/- 4 days) for the first 3 cycles, then every 2-4 weeks on subsequent cycles. The labs may be done more frequently than twice a week at the discretion of the treating physician and/or the PI.

^c TSH, free T3, free T4 will be done at least once monthly (+/- 4 days) after the start of therapy for the first 3 cycles, then every 3 months (+/- 4 days) on subsequent cycles.

^d Pregnancy test either urine or plasma should be done in women of childbearing potential 72 hours before initiation of protocol therapy.

^e Bone marrow aspiration must be done within 28-days (+/- 7 days) of initiation of therapy, then Day 28 (+/- 7 days) every 1-4 cycles. Cytogenetics may be used from prior bone marrow analysis if these were not reported on the screening bone marrow.

^f Correlative studies will be collected on peripheral blood at baseline (prior to 5-azacytidine dose), on day 14 (prior to avelumab), and between days 21 to 28 on cycle 1. Subsequently, peripheral blood will be obtained on days 1 and 14 of cycles 2, 4, 8, 12, and at progression if possible. All these tests can be +/- 5 days. Additional samples may be collected if the disease gets worse.

^g Correlative studies will be collected on bone marrow at baseline, day 28 (+/- 5 days), then on day 28 (+/- 5 days) of cycles 3, 7, 11 and at progression if possible.

^h EOS visits include a physical examination, CBC with differential and platelets and a limited chemistry profile (total bilirubin, serum creatinine, SGPT or SGOT). A bone marrow aspiration may be done if non-response or progressive disease cannot be unequivocally diagnosed from peripheral blood.

ⁱ Subject will be followed for toxicity for at least 30 days after the last protocol treatment. The 30-day follow-up visit (+ or - 3 days) will be scheduled as a

clinic visits for clinical evaluation and physical examinations. If the patient cannot make it to the MDACC clinic for this visit, the required follow up treatment procedures may be done with a local physician and the records forwarded to MDACC. The research nurse will contact the patient by telephone and get a verbal assessment of the patient's condition. The phone conversation will then be documented in the patient's charts.

^j Every 3-6 months for up to 5 years after last dose of study drug patient will have a physical exam and blood (about 1-2 teaspoons) will be drawn for routine testing. If the patient is unable to return to MD Anderson, they may be called by a member of the research staff and asked how they are feeling.

^k For patients that remain on study with no significant toxicity for more than 6 months, subsequent evaluations during study may be modified after discussion with the principal investigator. These include a decrease in frequency of bone marrow aspirations to every 6-12 months (or as clinically indicated), correlative studies to every 6-12 months (or suspension of sample collection for correlative studies), other laboratory tests to once every cycle.

^L [Perform at specified time-points and](#) repeat as clinically indicated

Data regarding adverse events will be collected during the study. Protocol specific data will be entered into PDMS/CORe. PDMS/CORe will be used as the electronic case report form for this protocol. While investigators do not need to report all adverse reactions, they must be recorded. The Principal Investigator will sign and date the AE log per each patient at the completion of each course. Following signature, the AE log will be used as source documentation for the adverse events for attribution.

Treatment may be discontinued for a variety of reasons, including patient withdrawal, investigator decision, and reasons specified by the protocol. Reasons for discontinuation of treatments are described in section 9.0.

8.0 CRITERIA FOR RESPONSE:

Response Criteria for AML

Responses will be assessed by the International Working Group for AML [67]. Responders are patients who obtain a CR, CRi, or PR, with or without cytogenetic response, hematologic improvements, and morphologic leukemia-free state.

Hematologic Improvement (HI): Hematologic response will be assessed by the MDS IWG response criteria (Cheson et al., Blood 2006)

- ◆ **Erythroid response (E)** (pretreatment Hgb <11 g/dL)
Hgb increase by ≥ 1.5 g/dL
- ◆ **Platelet response (P)** (pretreatment platelets <100 x10⁹/L)
Absolute increase of ≥ 30 x 10⁹/L for patients starting with > 20 x 10⁹/L platelets
Increase from < 20 x 10⁹/L to > 20 x 10⁹/L and by at least 100%
- ◆ **Neutrophil response (N)** (pretreatment ANC <1.0 x10⁹/L)
At least 100% increase and an absolute increase > 0.5 x 10⁹/L
- ◆ **Blast response (B)**
 $\geq 50\%$ reduction in peripheral blood or bone marrow blasts but still >5%

8 DISCONTINUATION OF TREATMENT:

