An Open-label Phase Ib/II Study of Avelumab in Combination with 5-azacytidine (Vidaza) for the Treatment of Patients with Refractory/Relapsed Acute Myeloid Leukemia
2016-0444

Core Protocol Information

Short Title	Avelumab (antiPDL1) and azacytidine in AML
Study Chair:	[name]
Additional Contact:	[name] [name] Leukemia Protocol Review Group
Additional Memo Recipients:	Recipients List OPR Recipients (for OPR use only) None Study Staff Recipients None
Department:	Leukemia
[contact]
Unit:	428
Study Manager:	[name]
Full Title:	An Open-label Phase Ib/II Study of Avelumab in Combination with 5-azacytidine (Vidaza) for the Treatment of Patients with Refractory/Relapsed Acute Myeloid Leukemia
Public Description:	N/a
Protocol Type:	Standard Protocol
Protocol Phase:	Phase I/Phase II
Version Status:	Terminated 10/03/2019
Version:	15
Document Status:	Saved as "Final"
Submitted by:	[name]--8/13/2019 10:24:00 AM
OPR Action:	Accepted by: [name] -- 8/22/2019 9:13:02 AM

Which Committee will review this protocol?

- The Clinical Research Committee - (CRC)

Avelumab and 5_azacytidine in AML_IST_(Final) 7.27.2018.doc

Protocol Body

An Open-label Phase Ib/II Study of Avelumab in
Combination with 5-azacytidine (Vidaza) for the Treatment
of Patients with Refractory/ Relapsed Acute Myeloid
Leukemia

Principal Investigator: [name].

Co-PI: [name], M.D.

Sponsor: University of Texas, MD Anderson Cancer Center

IND number: 131967

University of Texas

MD Anderson Cancer Center

Leukemia Department, Unit

1.1 **OBJECTIVES**

1.2 **Primary Objectives**

Part a. Phase IB

To determine the maximum tolerated dose (MTD) and dose limiting toxicity (DLT) of avelumab in combination with 5-azacytidine in patients with refractory/ relapsed acute myeloid leukemia (AML).

Part b. Phase II

To determine the overall response rate (ORR) defined as complete remission (CR/complete remission with incomplete platelet recovery (CRp)/complete remission with incomplete count recovery (CRi)/partial remission (PR)/hematologic improvement (HI)/morphologic leukemia free state (MLFS) of avelumab in combination with 5-azacytidine in patients with refractory/ relapsed AML.

1.3 **Secondary Objectives:**

1. To determine the number of patients who achieve > 50% reduction in blasts on therapy with this combination.
2. To determine the duration of response, disease-free survival (DFS), and overall survival

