3. (OS) of patients with refractory/ relapsed AML treated with this combination.

1.4 **Exploratory Objectives:**

1. To study immunological and molecular features at baseline and at predefined time-points on-therapy with avelumab and azacytidine in the peripheral blood and bone marrow to include (a) quantify immune ligand expression by the AML blasts and AML stromal components (MDSCs and MSCs) including 4-1BBL, ICOSL, PD-L1, PD-L2, OX-40L, CD137L and (b) determine the quantitative expression of positive and negative co-stimulatory molecules on individual T-lymphocyte subsets including 4-1BB, CTLA-4, ICOS, PD-1, OX40, LAG-3 and TIM-3, and (c) identify the immunophenotype of tumor-infiltrating T-lymphocytes (TILs) pre- and post-therapy with the combination: CD8+, CD4+ effector, or CD4+ regulatory.
2. To develop a micro-array based gene expression profile (GEP) predictor of response to anti-PDL1 and epigenetic therapy in AML.
3. To determine the correlation of responses to the combination with baseline cytogenetic and molecular abnormalities.

2.1 **BACKGROUND**

2.1.1 **Acute myeloid leukemia**

Approximately, 30-40% of adults with AML fail to achieve CR with 1 or 2 cycles of induction chemotherapy, and are deemed primary refractory. The outcomes of patients with acute myeloid leukemia (AML) who are refractory to induction therapy are dismal, with low

response rates to salvage chemotherapy and poor long-term survival¹⁻³. We have previously reported a dismal median OS of 3.8 months for patients with AML who are refractory to HiDAC-containing induction therapy (defined as $\geq 1\text{gm/m}^2$ cytarabine per dose)². Salvage therapy in such patient populations yielded a response rate of 18% and median response duration of 9 months.

These results emphasize the need to explore alternate salvage regimens for patients with relapsed/refractory AML. The development of novel and effective anti-AML agents and/or combinations is crucial to improving the outcome of AML.

2.1.2 Relapsed/Refractory AML:

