9.1.4 Follow-Up at Treatment Discontinuation or Early Withdrawal

Patients who discontinue treatment for any reason should complete end-of-treatment procedures when possible. End of treatment procedures will include a physical examination, CBC with differential and platelets and a limited chemistry profile (total bilirubin, serum creatinine, SGPT or SGOT). A bone marrow aspiration may be recommended only if non-response or progressive disease cannot be unequivocally diagnosed from peripheral blood. Although treatment will be discontinued at that time, all patients who do not withdraw consent for follow-up, die, or become lost to follow-up, will remain on study for follow-up evaluations. Subject will be followed for toxicity for at least 30 days after the last protocol treatment. The 30-day follow-up visit (+ or – 3 days) will be scheduled as a clinic visits for clinical evaluation and physical examinations. [The Subject will then be followed every 3-6 months for up to 5 years after the last dose of study drug.](#) If the patient cannot make it to the MDACC clinic for this visit, the required follow up treatment procedures may be done with a local physician and the records forwarded to MDACC. The research nurse will contact the patient by telephone and get a verbal assessment of the patient's condition. The phone conversation will then be documented in the patient's charts.

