All patients who received any dose of the study agent will be included in the analysis for efficacy and safety. Demographic/clinical characteristics (including duration of response) and safety data of the patients will be summarized using descriptive statistics such as mean, standard deviation, median and range. For the primary efficacy analysis, we will estimate the ORR for the combination treatment, along with the 95% credible interval. For the efficacy, a sample size of 40 patients ensures a posterior 95% credible interval for ORR of (0.17, 0.43), if the trial is not terminated early, under the assumption of a 30% ORR. Patients who drop out of the study before completing all the cycles will be treated as “failures” for the primary analysis. ORR during the study period will also be presented with the 95% confidence credible. The association between ORR and patient’s clinical characteristics will be examined by Wilcoxon’s rank sum test or Fisher’s exact test, as appropriate. Toxicity type, severity and attribution will be summarized for each patient using frequency tables.

The distribution of time-to-event endpoints (DFS and OS) including overall survival and progression free survival will be estimated using the method of Kaplan and Meier. Comparisons of time-to-event endpoints by important subgroups will be made using the log-rank tests. Paired t-tests will be used to determine the immunological and molecular changes in the peripheral blood and bone marrow from baseline to the time of response, and to the time of disease progression. Correlation analysis (such as logistic regression analysis) will be conducted to determine the relationship between induction of hypomethylation / DNA damage and clinical response.

A Toxicity Summary will be submitted to the IND Office Medical Monitor, after the first three patients have completed their first cycle of study therapy or administration is

discontinued, whichever comes first, and every three evaluable patients thereafter during the Lead-in Phase IB.

An Efficacy/Toxicity Summary will be submitted every five evaluable patients during **Phase II**.

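### Section 7.2.12 ties survival follow-up to objective response while 9.1.4 follows everyone; if the 7.2.12 qualifier is applied, Kaplan-Meier overall survival is biased upward.

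*Combined protocol and SAP*

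**What the plan says.** Section 1.3 lists as a secondary objective "To determine the duration of response, disease-free survival (DFS), and overall survival" of the patients treated with the combination. The Statistical Analysis Plan in section 11.2 takes every patient who received any dose as the efficacy set. It says time-to-event endpoints "including overall survival and progression free survival will be estimated using the method of Kaplan and Meier", and gives no censoring rule for OS.

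Follow-up after treatment is described in four places:

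- **Section 7.2.12:** "Patients with an objective response at completion of active study treatment will be followed for survival". The test is response status when active treatment is completed.
- **Continuation of 7.2.12, repeated as Table 6 footnote j:** "Every 3-6 months for up to 5 years after last dose of study drug patient will have a physical exam" and a routine blood draw, with a telephone call asking how the patient feels as the fallback. No responder limit is stated.
- **Section 9.1.4:** "all patients who do not withdraw consent for follow-up, die, or become lost to follow-up, will remain on study for follow-up evaluations", and then "The Subject will then be followed every 3-6 months for up to 5 years after the last dose of study drug". This covers everyone.
- **Table 6:** a Long-Term Follow-Up column at 3-6 month intervals, with no row for survival status. A footnote sets the minimum for every patient: "Subject will be followed for toxicity for at least 30 days after the last protocol treatment".

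**The concern.** The sections name two different follow-up populations for one endpoint. Only 7.2.12 says what the follow-up is for, namely survival, and it is the one that names responders. Section 9.1.4 speaks of evaluations in general.

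If the study team works from 7.2.12, a non-responder may have no scheduled contact after the 30-day toxicity visit. The same holds for a patient who responded and then relapsed before treatment ended, because the test is response at completion. Such patients would be censored for OS because their prognosis is poor, whereas Kaplan-Meier requires censoring unrelated to prognosis. The later part of the curve would then rest mainly on responders, and OS would look better than it is. The log-rank comparisons of subgroups planned in section 11.2 would use the same survival times.

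**Working it through.** **The plan's own figure.** The documents give no expected loss to follow-up and no OS figure for this regimen. The nearest design figure is the 95% credible interval for the response rate at 40 patients and 30% response, stated as (0.17, 0.43). With the beta(0.2, 1.8) prior and 12 responders in 40, the posterior is beta(12.2, 29.8), with interval (0.165, 0.435). It reproduces, so 30% of 40 is a fair base for the counts below.

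**Inputs from the documents.** Target response rate 30% and historical rate 10% (11.2); 40 Phase II patients, 52-58 in total (11.1); median OS 3.8 months in AML refractory to high-dose cytarabine induction (2.1.1 and 2.1.2); 30-day toxicity follow-up (Table 6 footnote).

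**Assumptions not in the documents.** Exponential survival; the 3.8-month median applied to non-responders; responder median 12 months (range 9 to 15); last contact with non-responders at month c = 3 (range 2 to 4).

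**Step 1: share outside 7.2.12.** This is 1 minus the response rate. At 30%: 0.70 × 40 = 28 of 40, or 36 to 41 of 52-58. At 10%: 36 of 40.

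**Step 2: share censored alive.** Non-responders who die before last contact are still counted as deaths, so the share lost is 0.70 × 2^(−c/3.8):

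- c = 2: 0.70 × 0.694 = 48.6%
- c = 3: 0.70 × 0.579 = 40.5%
- c = 4: 0.70 × 0.482 = 33.8%

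**Step 3: true OS.** S(t) = 0.30 × 2^(−t/12) + 0.70 × 2^(−t/3.8). Setting S(t) = 0.5 gives a median of 5.1 months. S(12) = 0.150 + 0.078 = 0.228.

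**Step 4: OS as Kaplan-Meier would report it.** Up to month 3 the curve is correct: S(3) = 0.252 + 0.405 = 0.657. After that only responders are at risk, so the estimate is 0.657 × 2^(−(t−3)/12).

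- Median: t = 3 + 12 × log2(0.657/0.5) = 7.7 months.
- 12-month OS: 0.657 × 2^(−9/12) = 0.391.

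**Step 5: sensitivity.** Over c = 2 to 4 and responder median 9 to 15 months, the reported median runs from 5.4 to about 11 months against a true 4.8 to 5.3.

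Fixing c for every patient is stylised, so the comparison was also simulated (200,000 patients per scenario). Responder median was 9 or 12 months, non-responder median 3.8 or 2.5, and last contact one month after treatment stopped. Results at 30% response:

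| Time to treatment stop in non-responders | Lost alive | Median overstated by | 12-month OS overstated by |
|---|---|---|---|
| Exponential, median 1 to 3 months | 24% to 46% | 0.3 to 2.5 months | 6 to 16 points |
| Fixed at 1, 2 or 3 months | 23% to 49% | 0 to 4.0 months | 10 to 20 points |

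With the 12- and 3.8-month medians and exponential stop times, the reported median is 7.6, 6.2 or 5.7 months (median stop 1, 2 or 3 months) against about 5.1. The 12-month estimate was too high in every scenario. The median was not: it is unchanged when it is reached before last contact.

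**The case against.** The strongest reply is that the protocol already follows everyone. Section 9.1.4 says so expressly. The continuation of 7.2.12, the Table 6 column and footnote j state no response condition. Section 7.2.12 is silent on non-responders and does not exclude them, so a team that obeys both sections follows all patients. Section 11.0 describes a single-center study, so the same staff are bound by both. Much of this stands: a reader might infer that the protocol restricts survival follow-up to responders only, and the documents do not say that. The effect is conditional on how 7.2.12 is applied.

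It does not remove the conflict. If everyone is meant, the qualifier in 7.2.12 has no function. The unrestricted sentence sits inside 7.2.12, so its patient can be read as the responder just described. None of the unrestricted passages names survival status as something to collect.

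Two other inferences should be resisted:

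- **That about 70% of patients would be lost.** That figure is 1 minus the target response rate, the share outside 7.2.12. Many of those patients would die while still observed.
- **That the plan compares OS with the poor historical survival in section 2.1.** It does not. The benchmark in section 11.2 is for response only.

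The size of the bias also rests on assumed survival and stopping times, and the 3.8 months comes from a refractory population, not from non-responders to this regimen.

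**Conclusion.** The inconsistency is real and should be corrected, but its effect is conditional. If the 7.2.12 qualifier governs practice, about 34% to 49% of all patients are censored alive for reasons tied to prognosis (23% to 49% under the wider assumptions), and OS is biased upward. The central illustration is a median of 7.7 against 5.1 months and 12-month OS of 39% against 23%. Over the simulated scenarios at 30% response, the median is overstated by 0 to about 4 months and 12-month OS by about 6 to 20 points. If 9.1.4 governs, no patient is censored because of response status and this bias does not arise.

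The damage is confined to secondary survival results. The response rate, its credible interval and the stopping rules do not use this follow-up.

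**What to change.** In 7.2.12, replace the opening qualifier with *All treated patients, whatever their response*, so that it agrees with 9.1.4 and footnote j. Add a row to Table 6, *Survival status (clinic or telephone)*, marked in the Long-Term Follow-Up column. Record date of death or date last known alive for every patient. In section 11.2, state that OS is censored at the date last known alive.

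The cost is one reworded sentence, one table row and one censoring rule. The extra work is a telephone or chart check every 3-6 months for patients not in response, which 9.1.4 already requires. Treatment does not change.
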